5.3 Sample size justification

5.3.1 Initial CMML Cohort

The primary aim of the initial CMML cohort was to evaluate the ORR for tipifarnib in CMML subjects with KRAS/NRAS wild type (biomarker-positive subgroup, referred to below as "pos-subgroup"; and in CMML subjects with KRAS and/or NRAS mutations referred to as the "neg-subgroup"; those two subgroups comprise the entire population sampled in the trial. This trial is planned as a single treatment trial with statistical comparison to historical ORR rate 0.10 (10%). The statistical objective is to provide evidence that the TRUE underlying ORR in all subjects and/or in the pos-subgroup exceeds 0.10.

Prior data on tipifarnib in CMML subjects with unknown NRAS and KRAS mutational status yielded ORR~0.20. Non clinically, it has been demonstrated using a large panel of cell lines that Ras wild-type cell lines are more sensitive to tipifarnib than Ras mutant lines (End 2001), therefore it could be possible that subjects with both KRAS and NRAS wild type may be more sensitive to tipifarnib therapy. The availability of prior data suggests that use of Bayesian statistics, which can incorporate use of the prior information to yield more precise statistical estimates of response rates than traditional methods that rely only on data to be observed in the prospective trial. Thus, the probability that the TRUE underlying ORR exceeds 0.10 (i.e., success criteria) can be computed from the observed data, assuming a prior estimated TRUE ORR from the prior data. This probability is referred to as "posterior probability" in Bayesian analysis, since it is estimated from the observed data incorporating the prior estimate. If this probability is high (e.g., at least 0.80, i.e., meets the success criteria; probability of meeting the success criteria is referred to as "PoS"), then it can be concluded that the TRUE ORR exceeds 0.10, i.e., that the success criteria is met.

The probability that OR exceeds 0.10 was computed for several potential scenarios to span the range of potential designs and design outcomes:

- Success Criteria: Probability that TRUE rate >0.10 is at least 0.80
- Assumed TRUE underlying ORR = 0.2, 0.3, 0.4 (0.2 useful for evaluating the entire population, 0.4 and 0.3 for evaluating the pos-subgroup)
- Sample Sizes: 10, 20
- Prior ORR = 0.3 (as a conservative estimate for the pos-subgroup)
- Prior data influence (measured by assumed sample size "N" that yielded the prior data)
 - = 1 (to minimize the influence of the prior data on the PoS estimate, i.e., to let the observed data drive the estimate), and

- o = 10 (to limit the influence of the prior data to an amount equal to the smallest reasonable sample size of observed data, which is N=10)

These probabilities are in Table 1. For example, after ORR is observed in 10 subjects, if the TRUE ORR is 0.3, there is 0.85 PoS prior ORR estimate 0.3 with minimal (N=1) prior information; this result is highlighted in yellow in Table 6. If the assumption on prior information is increased to N=10, PoS increases to 0.97, which is akin to over 95% power; this result is highlighted in green in Table 6. PoS increases if TRUE ORR is higher (values for 0.4 are shown in Table 6), and decreases if TRUE ORR is lower (values for 0.2 are shown in Protocol Table 6). Thus, assessment using N=10 for the pos-subgroup yields sufficient power / precision based on assumed ORR on par with prior AML data. Table 6 also shows the corresponding values for N=7 for prior ORR based on N=1 and on N=7; NOTE that N=7 prior is used instead of N=10 since the prior assumption is given equal weight as the observed sample size.

Table 1: Probability of success for various sample sizes

Declare Success if prob.(TRUE rate>0.1) at least:	Prior Overall Response Rate Assumed	Probability of Success after N=10 if TRUE rate is:			Probability of Success after N=7 if TRUE rate is:		
		0.2	0.3	0.4	0.2	0.3	0.4
0.8	0.30 (N=1)	0.62	0.85	0.95	0.43	0.66	0.84
	0.30 (N=10 or 7)	0.9	0.97	>0.99	0.78	0.93	0.97

When assuming prior ORR=0.3 from prior N=10, observing at least 1 response from 10 subjects will meet the success criteria. When assuming N=1 for prior ORR=0.3, at least 2 responses from 10 subjects will meet the success criteria. For assumed prior from N=7, at least 1 responses from 7 subjects will meet the success criteria; for assumed prior from N=1, at least 2 responses from 7 subjects will meet the success criteria.

5.3.2 Amendment 3 Cohorts: MDS/MPN and AML

The cohorts introduced in amendment 3 employ a 2-stage design. In the first stage, 28 eligible subjects (7 subjects per cohort in Stage 1) will be enrolled and stratified into one of four neoplasia and biomarker-defined cohorts based on diagnosis and subject CXCR4/2 expression ratio level (high vs low) determined from a bone marrow sample. Each cohort will be terminated if 0 responses are observed at end of first stage. Otherwise, an additional 11 subjects will be enrolled for the second stage.

At the completion of a two-stage cohort, the cohort will be considered as failed if there are 3 or less responses out of 18 evaluable subjects, indicating the true ORR is 10% or less. If there are 4 or more responses, the treatment will be considered of further interest indicating the true ORR is higher than 10%.

For this two-stage study design, a null response rate of 10% and alternative response rate of 30% are assumed. It provides 80% power to detect a difference between 10% and 30% ORR at one-sided significance level of 0.089. Using this design, the probability of terminating the cohort at the end of first stage is 0.48 if the true ORR is 10% or less while the probability of terminating the cohort at the end of first stage is 0.13 if the true ORR is 30%.

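### Three or fewer responses in 18 does not indicate a true ORR of 10% or less; the plan should say only that an ORR above 10% was not shown

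*SAP*

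**What the plan says.** SAP 5.3.2 sets one two-stage rule for each Amendment 3 cohort. Seven subjects enter stage 1. "Each cohort will be terminated if 0 responses are observed at end of first stage". A cohort with at least one response goes on to a second stage of 11 more, making 18. A completed cohort with 4 or more responses is of further interest. A completed cohort fails with "3 or less responses out of 18 evaluable subjects, indicating the true ORR is 10% or less".

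The same wording stands in Protocol 12.3 and in the Statistical Methods part of the Protocol Synopsis.

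On the planning values, the SAP says that "a null response rate of 10% and alternative response rate of 30% are assumed" and adds: "It provides 80% power to detect a difference between 10% and 30% ORR at one-sided significance level of 0.089". Neither document gives operating characteristics for true rates between 10% and 30%, and neither says that missing the boundary means only that the 10% null was not rejected.

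SAP 10.2 separately requires the ORR to be presented with a two-sided 95% Clopper-Pearson interval.

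**The concern.** The boundary of 4 in 18 tests whether the ORR exceeds 10%. Missing it means that the test did not reject. The plan goes further and states in advance that the true rate is then 10% or less. With 18 subjects and 80% power at 30%, the design cannot carry that statement, because rates well above 10% often produce 3 or fewer responses.

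Amendment 3 was written to test prospectively whether a high CXCR4/2 ratio goes with response, and each cohort receives its own verdict. I found no planned comparison of ORR between the high and low cohorts. If the high-ratio MDS/MPN cohort had 4/18 and the low-ratio cohort 3/18, the plan's words would describe one as above 10% and the other as 10% or less, for a difference of one response.

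**Working it through.** **Inputs (SAP 5.3.2; same values in Protocol 12.3).** Stage 1 has n1 = 7, with a stop at 0 responses. Stage 2 adds n2 = 11. Success is 4 or more of 18. Null 10%, alternative 30%, one-sided alpha 0.089, power 80%, probability of a stage 1 stop at 10% of 0.48.

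The true rates 15%, 20% and 25% are scenarios chosen here between the null and the alternative. They are not planning values for these cohorts. The 20% point has a basis in SAP 5.3.1: "Prior data on tipifarnib in CMML subjects with unknown NRAS and KRAS mutational status yielded ORR~0.20", and the MDS/MPN cohorts include CMML.

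**Formulas (exact binomial, true rate p).**
- Stop at stage 1: S(p) = (1 − p)^7
- Completes 18 with 3 or fewer responses, and so gets the label: L(p) = sum over x = 1, 2, 3 of P(Bin(7, p) = x) × P(Bin(11, p) ≤ 3 − x)
- Total negative = S + L; success = 1 − S − L
- Label among cohorts reaching stage 2: L / (1 − S)

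**Reproducing the plan.** Success at 10% is 0.0893 (stated 0.089). Success at 30% is 0.8000 (stated 80%). S(10%) = 0.9^7 = 0.478 (stated 0.48). A single-stage rule of 4 in 18 would give alpha 0.098 and power 0.835, which do not match, so the two-stage calculation is the one the plan used. The plan's 0.13 for a stage 1 stop at 30% does not reproduce (0.7^7 = 0.082). That is a separate matter and does not enter this check.

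**Example at p = 0.20.**
- S = 0.8^7 = 0.2097
- x = 1: 0.3670 × 0.6174 = 0.2266
- x = 2: 0.2753 × 0.3221 = 0.0887
- x = 3: 0.1147 × 0.0859 = 0.0099
- L = 0.2266 + 0.0887 + 0.0099 = 0.325
- L / (1 − S) = 0.3251 / 0.7903 = 0.411

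**All rates.**

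| True ORR | Stopped at 0/7 | Completed, ≤3/18 (label) | Total negative | Success | Label, given stage 2 |
|---|---|---|---|---|---|
| 10% | 0.4783 | 0.4324 | 0.9107 | 0.0893 | 0.8288 |
| 15% | 0.3206 | 0.4219 | 0.7425 | 0.2575 | 0.6210 |
| 20% | 0.2097 | 0.3251 | 0.5348 | 0.4652 | 0.4114 |
| 25% | 0.1335 | 0.2105 | 0.3440 | 0.6560 | 0.2429 |
| 30% | 0.0824 | 0.1176 | 0.2000 | 0.8000 | 0.1282 |

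Across all cohorts started, the label is almost as likely at a true ORR of 15% (0.42) as at 10% (0.43).

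**What a failing result looks like.** A completed cohort has at least one response, so it can fail only with 1, 2 or 3. Clopper-Pearson 95% limits for x of 18 are the 2.5% quantile of Beta(x, 19 − x) and the 97.5% quantile of Beta(x + 1, 18 − x). These ignore the two-stage design.

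| Responses | Observed ORR | 95% interval |
|---|---|---|
| 1/18 | 5.6% | 0.1% to 27.3% |
| 2/18 | 11.1% | 1.4% to 34.7% |
| 3/18 | 16.7% | 3.6% to 41.4% |

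Every upper limit is well above 10%. Two of the three observed rates exceed 10%, and the intervals for those two contain 30%.

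**The case against.** The strongest reply is that the operative decision is only failed versus of further interest, as is usual for a two-stage phase 2 design, and that the clause on the true ORR is a gloss in the sample-size text. The primary analysis in SAP 10.2 does not use it: a 3/18 cohort would be presented as 16.7% with its interval. The 20% chance of a negative outcome at a true ORR of 30% is also disclosed, since it is the complement of the stated power. SAP section 4 adds that AML enrolment was held and that the study report covers CMML and MDS/MPN only, so at most one low-CXCR4/2 cohort is affected in practice.

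Most of this stands, and it limits the point to wording. It does not remove it. The clause is the plan's stated meaning of failure in three places, and it would sit beside an interval reaching 41.4%.

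Two stronger readings are tempting, and the documents do not support either.
- A reader might infer that a cohort with true ORR 20% is labelled 10% or less 53% of the time. That figure is the total negative probability and includes the 21% stopped at 0/7. The clause applies only to completed cohorts; those stopped at stage 1 are simply terminated. The label itself has probability 33%, or 41% given stage 2.
- A reader might infer that the plan will report the low-ratio cohort as inactive and rest the biomarker claim on that. No section says so. The only formal high-versus-low comparison is the Cox model and log-rank test under survival in SAP 10.3.4.

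**Conclusion.** The inference is unsupported as written and should be corrected. A completed cohort with a true ORR of 15%, 20%, 25% or 30% is described as having 10% or less with probability 42%, 33%, 21% or 12% of all cohorts started (62%, 41%, 24% or 13% of those reaching stage 2). The total probability of a negative outcome, by either route, is 74%, 53%, 34% and 20%.

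These figures assume independent responses, one true rate across both stages, and exactly 7 and then 18 evaluable subjects. The intermediate true rates are illustrative. The conclusion does not depend on them, because the plan's own 80% power already implies a 20% negative rate at 30%.

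The fault lies in the stated meaning of failure. The boundary, alpha and power are internally consistent and are not in question.

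**What to change.** In SAP 5.3.2, Protocol 12.3 and the Protocol Synopsis (Statistical Methods), keep the verdict that the cohort has failed. Replace the clause about the true ORR with: *the data do not provide sufficient evidence that the true ORR exceeds 10%*. All three places must change together, or the Protocol will contradict itself.

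Add that the verdict is read alongside the ORR and 95% interval already required by SAP 10.2; no new analysis is needed. Do not describe a failed cohort, including the low-CXCR4/2 MDS/MPN cohort, as having an ORR of 10% or less.

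The cost is one clause in the SAP and two in the Protocol, and a weaker negative conclusion. Boundary, sample size, alpha (0.089) and power (80%) stay as they are.

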5.3.3 Replacement of Subject

Subjects who do not receive at least one dose of tipifarnib will be replaced. Subjects who do not have at least one post baseline disease assessment will be replaced.

5.4 Treatment randomization

This trial is planned as a single treatment trial; no randomization will be used.

6. GENERAL ANALYSIS DEFINITIONS

6.1 Study period and visit window definitions

6.1.1 Study periods

The study includes the following time and events schedules: screening (Day -28 to Day -1), Day 1, Day 15, and Day 25 of each cycle (28 days per cycle), End of Treatment visit (30 ± 7 days from the last dose of tipifarnib or immediately before the initiation of any other anticancer therapy), Follow up visit, Follow up contact. A detailed description of the time and events schedule of planned study assessments and visit procedures is outlined in Protocol Table 1.

6.1.2 Baseline, study day, and visit windows

Analyses requiring use of baseline data will use the last information collected pre-dose on or prior to first dosing on Day 1. Baseline assessments may be taken during screening if Day 1 pre-dose assessments are not available.

Subject's time on study will be determined in Study Days. The study day is defined as the number of days since or prior to the first dose date of tipifarnib. The day of the first dose of tipifarnib is defined as Day 1 while the last day prior to Day 1 is defined as Day -1.

Visit windows will not be used for this study.

6.2 Protocol deviations

████████ will provide a complete list of all identified deviations to Kura. The Sponsor will categorize the deviations.

6.3 Study populations

6.3.1 Full analysis set

The Full Analysis Set (FAS) is defined as all subjects who received at least one dose of tipifarnib in this study. It is the primary population for the safety analysis

6.3.2 Per protocol analysis set

The Per Protocol Analysis Set (PPS) includes subjects who received at least one dose of tipifarnib, and have a baseline disease assessment and at least one post baseline disease assessment. It is the primary population for the efficacy analysis.

6.4 Treatment assignment and treatment groups

Prior to protocol amendment 3.0, all eligible subjects with CMML were assigned to receive tipifarnib 1200 mg to be taken orally with food bid for 7 days in alternating weeks (days 1-7 and days 15-21) in 28-day cycles. Additionally, stepwise 300 mg dose de-escalation based on subject tolerability is allowed. In amendment 3.0, all eligible subjects will be assigned to receive tipifarnib 400 mg to be taken orally with food on days 1-21) in 28-day cycles. Additionally, stepwise 100 mg dose de-escalation based on subject tolerability is allowed.

6.5 Subgroups

For demography, baseline characteristics and efficacy, 4 subgroups will be presented:

1. Subjects with CMML and KRAS/NRAS wild type
2. Subjects with CMML and KRAS/NRAS mutation
3. Subjects with MDS/MPN and high CXCR4/2 ratio
4. Subjects with MDS/MPN and low CXCR4/2 ratio

In CMML efficacy analyses, additional 6 subgroups will be presented:

1. Subjects with CMML1 and KRAS/NRAS wild type
2. Subjects with CMML1 and KRAS/NRAS mutation
3. Subjects with CMML2 and KRAS/NRAS wild type
4. Subjects with CMML2 and KRAS/NRAS mutation
5. Subjects with CMML and high CXCR4/2 ratio
6. Subjects with CMML and low CXCR4/2 ratio

The total for each of CMML and MDS/MPN will be summarized.

6.6 Global analysis and reporting rules

Data will be summarized using standard summary statistics and additional descriptive methods including individual data listings and plots of individual data and summary statistics. For continuous variables, summaries will include the number of non-missing subjects, mean, standard, median, minimum, and maximum. For categorical variables, summaries will present the number and percentage of subjects in each subgroup or category.

7. DEMOGRAPHIC AND BASELINE CHARACTERISTICS

Unless specified otherwise, subject baseline demographics and disease status variables will be summarized on the full analysis set.

Baseline Demographics summary will include the following:

- Age in years, will be calculated as INT [(date of informed consent - date of birth)/365.25], where INT is the integer value of the calculation.
- Sex (male or female)
- Race (white, black or African American, native Hawaiian or other Pacific Islander, Asian, American Indian or Alaska Native, other, not reported)
- Ethnicity (Hispanic or Latino, not Hispanic or Latino, not reported)
- Height in cm
- Weight in kg

Subject disease status will be summarized among the following items:

- Time since diagnosis in months (calculated relative to the date of consent signed)

- Disease diagnosis (CMML-1, CMML-2, MDS/MPN, and AML)
- Any prior anti-cancer therapy (Yes, No)
- Baseline ECOG performance status (0, 1)

All demographic and baseline characteristic data including disease history, medical history, and surgical history will be presented in the subject data listings.

8. SUBJECT DISPOSITION

The frequency and percent of subjects who terminate the treatment, complete the study, discontinue the study prior to completion will be summarized.

Reasons for terminating the study treatment include:

- Adverse event
- Death
- Physician's decision
- Study terminated by sponsor
- Progressive disease
- Subject non-compliance/protocol violation
- Withdrawal of consent
- Other

Reasons for early discontinuation of the study include:

- Completed
- Adverse event
- Death
- Lost to follow up
- Permanent withdrawal of consent
- Physician decision
- Pregnancy
- Protocol defined disease progression
- Study terminated by sponsor
- Subject non-compliance / protocol violation
- Other

The disposition data will be listed for all subjects.

9. DRUG EXPOSURE AND TREATMENT

9.1 Drug exposure

The following parameters will be summarized:

- Duration of treatment (weeks) is defined as: (the date of last dose of tipifarnib - date of first dose tipifarnib + 1)/7.
- The number of planned doses is defined as the total planned AM and PM dose before treatment discontinuation.
- The number and percent of planned dosing is defined as the number of actual doses/the number of planned dosing time) *100.
- The number and percentage of subjects skipping doses (AM or PM dose) before treatment discontinuation.
- Daily Dose (mg) is defined as the cumulative dose/duration of treatment (day) before treatment discontinuation.
- The number and percentage of subjects experiencing any vomited dose before treatment discontinuation.

Drug treatment and exposure parameters will be listed.

9.2 Prior and concomitant medications

Prior and concomitant medications will be coded using the WHO Drug dictionary June 2016. Medications initiated prior to start of treatment and maintained during the study or initiated after start of treatment will be considered as concomitant medications. Medications administrated prior to and not continuing the study treatment will be considered as prior medications. Medications with partial or missing start date will be assumed to be concomitant medications, unless there is clear evidence (through comparison of partial dates or end date with the date of tipifarnib treatment) to suggest that the medications are not taken during study. Prior and concomitant medications will be summarized separately by anatomical therapeutic class (ATC) and preferred name. The by-subject listing for all prior/concomitant medications will be provided.

9.3 Other treatments/procedures and transfusions

Data of non-drug treatment/procedures, subsequent anti-cancer therapy, transfusions will be listed, but will not be summarized.

10. EFFICACY ANALYSES

The efficacy analyses will be performed on the Per Protocol Analysis Set.

10.1 Definition of endpoints

Disease assessments other than bone marrow (hematology and quality of life evaluations) will be performed at screening, and at the Day 25 visit (\pm 5 days) performed during Cycles 2, 4, 6, 9 and every approximately 12 weeks thereafter (Cycles 9, 12, 15, etc.), at the End of Treatment visit and during Follow Up. Bone marrow evaluation will be performed as part of the disease assessment at screening and at the Day 25 visit (\pm 5 days) performed during Cycles 2, 4, 6 and 9. Thereafter, bone marrow evaluations will occur during disease assessments in accordance with institutional standard practice. Hematologic assessments, including peripheral blood evaluations and review of transfusion requirements, will be performed at screening and at least

monthly until disease progression. Additional disease or hematologic assessments may be conducted if deemed necessary by the Investigator.

For subjects with CMMI and MDS/MPN, determination of disease response will be performed by the Investigator according to the MDS/MPN IWG criteria (Protocol Table 9 and 10); Objective Response (OR) is achieved if the investigator indicates complete response, complete cytogenetic remission, partial remission, marrow response, or clinical benefit.

10.2 Efficacy analyses for the primary endpoint

The primary objective of the study is to assess the antitumor activity of tipifarnib. Objective Response Rate (ORR) will be estimated based on the crude proportion of subjects who achieve an objective response (as defined in section 10.1). ORR will be presented with a two-sided 95% confidence interval (CI) using the Clopper-Pearson method. For the CMMI subjects, Bayesian posterior probabilities that TRUE underlying rates exceed several meaningful levels of response rate (e.g., exceeding 0.1 for the primary endpoint ORR) will be computed. Informative and uninformative prior distributions of rates will be used. Traditional 90% confidence intervals for TRUE underlying rates will also be computed and reported.

10.3 Efficacy analyses for the secondary endpoints

10.3.1 Rate of Best Response

The disease response of CMMI and MDS/MPN will be ordered in the sequence of Complete Response, Complete Cytogenetic Remission, Partial Remission, Marrow Response, Clinical Benefit, Stable Disease, and Progressive Disease. The best response will be presented with a two-sided 95% CI using the Clopper-Pearson method.

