## **7 SUBJECT SELECTION**

### **7.1 Inclusion Criteria**

For inclusion of a subject in the study, all of the following inclusion criteria must be fulfilled:

1. Subject is at least 18 years of age.
2. For subjects to be enrolled in the CMML or MDS/MPN expansion cohorts:
  - a. Diagnosis of CMML or MDS/MPN as defined by the World Health Organization (WHO) criteria (2008).
3. For subjects enrolled in the AML cohort:
  - a. Documented pathological evidence of AML, as defined by WHO criteria (2008)
  - b. Refractory to previous induction chemotherapy, relapsed disease, or age  $\geq 60$  and not appropriate for standard cytotoxic therapy due to age, performance status, and/or adverse risk factors according to the treating physician
4. Eastern Cooperative Oncology Group (ECOG) performance status 0 - 2.
5. Subject is willing and able to comply with scheduled visits, treatment plans, laboratory tests and other procedures (including bone marrow assessments).
6. At least 1 week since the last systemic therapy regimen prior to Cycle 1 Day 1. Subjects on a stable dose of hydroxyurea for at least 2 weeks prior to Cycle 1 Day 1 may continue on hydroxyurea until Cycle 1 Day 14. Subjects must have recovered to NCI CTCAE v. 4.03 < Grade 2 from all acute toxicities (excluding Grade 2 toxicities that are not

considered a safety risk by the Sponsor and Investigator) or toxicity must be deemed irreversible by the Investigator.

7. Acceptable liver function:
  - a. Total bilirubin  $\leq$  upper limit of normal (ULN).
  - b. AST (SGOT) and ALT (SGPT)  $\leq 1.5 \times$  ULN.
8. Acceptable renal function with serum creatinine  $\leq 1.5 \times$  ULN or a calculated creatinine clearance  $\geq 60$  mL/min using the Cockcroft-Gault or Modification of Diet in Renal Disease formulas.
9. Female subjects must be:
  - a. Of non-child-bearing potential (surgically sterilized or at least 2 years post-menopausal); or

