# **11                        STUDY PROCEDURES**

## **11.1                    Screening and Baseline Assessments**

A signed Informed Consent Form (ICF) must be obtained before any study-specific screening evaluations are performed and should be documented in the subject's medical chart.

The following evaluations and procedures will be performed within 28 days prior to the first study drug administration (Cycle 1 Day 1). Any screening evaluation, including disease status, will need to be repeated if performed more than 28 days from Cycle 1 Day 1. Evaluations performed as part of the standard of care within 28 days of dosing but prior to consent, do not need to be repeated. By signing the consent form, the subject agrees to the collection of this health information.

- Obtain signed ICF and form for the HIPAA/Data Protection Act
- Record subject's medical history, including demographics, primary diagnosis and WHO classification, outcome and duration of response to prior cancer therapy and any ongoing AEs
- Record concomitant medications
- Record subject weight
- Record subject height

- Perform bone marrow aspirate for disease assessment, cytogenetic assessment and RNA bone marrow biomarker analysis.
- In MDS/MPN subjects, complete symptom assessment as per the myeloproliferative neoplasm symptom assessment form total symptom score (MPN-SAF TSS, Emmanuel 2012)
- Record the number of RBC, whole blood and platelet transfusions for the 4 months prior to Cycle 1 Day 1.
- Collection of buccal swabs. If swabs are not collected at screening for any reason, collection can be conducted at any time during the study.
- Blood sample for NGS oncogene panel sequencing including KRAS, NRAS. Subjects with known wild type KRAS, NRAS status can be enrolled in the study prior to receiving the outcome of the oncogene panel test; however, if wild type RAS status is not confirmed in the NGS panel test, the subject will be replaced and continuation of treatment should be discussed with the Sponsor.
- 

The following evaluations and procedures will be performed within 14 days prior to the first administration of study drug (Cycle 1 Day 1):

- Complete physical examination including vital signs (heart rate, blood pressure, temperature)
- Assess ECOG performance status.
- Perform hematology tests (hemoglobin, platelets, WBCs, neutrophils, neutrophil precursors, lymphocytes, monocytes and blasts)

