5.1.2 Secondary objectives and endpoints

Secondary Objective: To assess the effect of tipifarnib on the following:

- Rate of CR, complete cytogenetic remission, partial remission, marrow response, and clinical benefit
- Duration of Response
- Rate of PFS at 1 year
- Rate of survival at 1 year
- AE profile according to NCI CTCAE v 4.03

Secondary Endpoint: Response assessments according to the MDS/MPN IWG criteria (MDS/MPN and CMML) or International Working Group criteria (AML cohorts); treatment emergent adverse events (TEAEs) and serious adverse events (SAEs) evaluated according to NCI CTCAE v.4.03.

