11.7 Cytogenetics

Cytogenetics data will be listed by assessment and subject.

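### The complete cytogenetic remission rate is taken over the whole per-protocol set, so it cannot exceed the share of subjects with abnormal baseline cytogenetics, and that share is not tabulated

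*SAP*

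**What the plan says.** SAP 5.1.2 lists among the secondary objectives "Rate of CR, complete cytogenetic remission, partial remission, marrow response, and clinical benefit". Protocol section 6.2 lists the same rates.

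SAP 10.3.1 treats CCR as one level of a single best-response variable, "ordered in the sequence of Complete Response, Complete Cytogenetic Remission, Partial Remission, Marrow Response, Clinical Benefit, Stable Disease, and Progressive Disease". On the interval it says: "The best response will be presented with a two-sided 95% CI using the Clopper-Pearson method". It states no denominator of its own. That comes from SAP 10: "The efficacy analyses will be performed on the Per Protocol Analysis Set". SAP 6.3.2 admits to that set subjects who took at least one dose and "have a baseline disease assessment and at least one post baseline disease assessment". Protocol section 7.1 admits CMML and MDS/MPN subjects on a WHO diagnosis. An abnormal karyotype is required in neither place.

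Baseline cytogenetics are collected. Protocol section 11.1 has at screening: "Perform bone marrow aspirate for disease assessment, cytogenetic assessment and RNA bone marrow biomarker analysis". Their only stated use in the analysis is in SAP 11.7: "Cytogenetics data will be listed by assessment and subject". They are not among the baseline disease variables summarised under SAP 7. SAP 6.5 shows efficacy by RAS status in CMML and by CXCR4/2 ratio in MDS/MPN.

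**The concern.** A cytogenetic remission presupposes an abnormality to clear. A subject with normal cytogenetics at screening adds one to the denominator and cannot add to the numerator. The tabulated rate therefore mixes two things: how often tipifarnib clears an abnormality, and how many subjects had one.

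With cohorts of up to 18, the second part can move a good deal by chance. The planned tables would not show this, because baseline cytogenetics appear only in a by-subject listing. What is at stake is the reading of one descriptive secondary rate, overall and side by side in the marker groups.

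The numerator has a related problem. Best response is ordered and CCR ranks below complete response, so a subject who achieves both is counted only under complete response. The CCR line is then not the count of subjects who achieved CCR.

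**Working it through.** The plan states no CCR rate and no assumed share of subjects with abnormal cytogenetics, so there is no figure of its own to reproduce.

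**Inputs**
- Completed cohort size: 18 (SAP 5.2, 5.3.2).
- Evaluable CMML subjects: 9 RAS wild type and 7 RAS mutant (SAP 4).
- Denominator: the PPS (SAP 10, 6.3.2).
- Share with an abnormal baseline: not in the documents. Assumed range one third to two thirds, with 1 as the no-dilution case.
- Number of remissions: 2, for illustration only.

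**Step 1: the cap.** Leave the numerator problem aside and count every CCR. Let m be the number abnormal at baseline and q the CCR rate among them. Then

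PPS rate = (m / 18) × q, which is at most m / 18.

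With m = 6, 9 or 12 the ceiling is 33%, 50% or 67%.

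**Step 2: 2 remissions in a cohort of 18** (Clopper-Pearson, 95%)

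| Denominator | Rate | Interval |
|---|---|---|
| PPS, 18 | 11.1% | 1.4 to 34.7 |
| 12 abnormal | 16.7% | 2.1 to 48.4 |
| 9 abnormal | 22.2% | 2.8 to 60.0 |
| 6 abnormal | 33.3% | 4.3 to 77.7 |

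If all 18 are abnormal, nothing changes. Over the assumed range the ratio of restricted to PPS rate is 18/12 = 1.5 up to 18/6 = 3.

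**Step 3: two marker groups of 18 with the same q = 1/3**

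| Abnormal, group A v group B | PPS rates |
|---|---|
| 9 v 9 | 16.7% v 16.7% |
| 6 v 12 | 11.1% v 22.2% |
| 3 v 12 | 5.6% v 22.2% |

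Equal shares give equal, though diluted, rates. Unequal shares give unequal rates with no difference in q.

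**Step 4: how easily the shares could differ.** Suppose both groups have the same true abnormal share p. Sum the product of the two binomial probabilities over all pairs of counts whose observed shares differ by at least 20 percentage points. For p from 30% to 50% the probability is 20% to 24% for 18 v 18, and 39% to 45% for 9 v 7. Values above 50% mirror those below.

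**The case against.** The strongest reply is that SAP 10.3.1 describes a best-response distribution. Each subject falls in one of seven ordered categories. A common denominator makes the categories sum to 100% and the top five sum to the objective response rate of SAP 10.1 and 10.2. The share of PPS subjects whose best response is CCR is a valid quantity. This stands, and it is why the table should stay as it is. It does not supply the CCR rate promised in SAP 5.1.2 for those in whom CCR is possible.

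Second, CCR is defined by reference to Protocol Tables 9 and 10, which are not visible in the public text. That normal-karyotype subjects cannot achieve it rests on the ordinary meaning of the term. This stands as a stated assumption.

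Third, a reader might infer that the rates are not comparable between marker groups, or that an imbalance would pass for a treatment difference. The documents support neither. Non-comparability needs a difference in the abnormal share, and no such figure is given. Every subject receives tipifarnib and there is no comparator (Protocol 9.7, SAP 5.4). No contrast of CCR by marker is planned: the hazard ratios and log-rank p-value sit under survival in SAP 10.3.4. For RAS status the worry is weaker still. No response of any kind was seen in the 7 evaluable RAS-mutant subjects, and CCR is a component of objective response, so their CCR rate is zero over any non-empty denominator.

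Fourth, the listing in SAP 11.7 would allow a restricted rate to be worked out afterwards. That is true, but the definition would then be chosen with the results in view.

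**Conclusion.** The point holds as a minor one. As planned, the CCR rate is taken over all PPS subjects. It is capped at the share with an abnormal baseline and may differ between marker groups if that share differs by chance.

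The size is unknown because the share is unknown. With one third to two thirds abnormal, the restricted rate is 1.5 to 3 times the PPS rate. If every subject is abnormal at baseline, the two coincide. A reader might take some such multiple as the amount by which this trial understates CCR, but the documents give nothing to fix it. The multiple also applies only when every CCR is counted, which the ordered variable does not do when complete response and CCR coincide.

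The conclusion rests on the ordinary meaning of cytogenetic remission and on at least one PPS subject having normal screening cytogenetics. The primary objective response rate and the 4-of-18 rule are untouched, since subjects with normal cytogenetics can respond in other categories.

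**What to change.** Keep the ordered best-response table on the PPS. In SAP 10.3.1 add a separate CCR rate with a Clopper-Pearson interval, specified as follows:

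- **Denominator:** PPS subjects with an abnormal screening cytogenetic result.
- **Numerator:** every such subject who achieves CCR, including those whose best response is complete response.
- **Missing results:** subjects with no post-baseline cytogenetic result count as not achieving CCR, and their number is shown.

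Add to SAP 7 a table of baseline cytogenetics (normal, abnormal, not available) by the subgroups of SAP 6.5.

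The cost is SAP wording, one extra rate, one baseline table and a flag derived from data already collected. Conduct, sample size and the decision rule do not change. The downside is a smaller denominator and a wider interval for this one descriptive rate: in the illustration with 6 abnormal subjects, 4.3 to 77.7 in place of 1.4 to 34.7.
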